In SG035-0003, a phase 2, single-arm, open-label study in patients with relapsed or refractory HL postASCT, and in SG035-0004, a phase 2 trial conducted in patients with relapsed or refractory sALCL, brentuximab vedotin was administered at a dose of 1.8 mg/kg every 3 weeks. One hundred two patients with relapsed and refractory HL and 58 patients with relapsed and refractory sALCL were exposed for a median duration of approximately 27 weeks (9 cycles) and 20 weeks (6 cycles), respectively. The primary endpoint of both studies was overall response rate. Treatment-emergent AEs occurring in $\geq 20\%$ of patients in phase 2 were peripheral sensory neuropathy (44%), fatigue (42%), nausea (41%), diarrhoea (34%), pyrexia (31%), upper respiratory tract infection (28%), neutropenia (21%) and vomiting (20%). These events were primarily mild to moderate in severity and reversible. Approximately half of patients had treatment-emergent peripheral neuropathy, predominantly sensory neuropathy, with an onset and severity pattern consistent with a cumulative effect of exposure. Dose delay and subsequent reduction to 1.2 mg/kg was generally effective in managing peripheral neuropathy. Moderate or severe neutropenia occurred in 13% and 7% of patients, respectively; these events were typically of short duration and well managed by brief dose delays with growth factor support in some cases. Infusion-related reactions occurred in approximately 10% of patients and were typically managed by dose delay or reduction. The clinical laboratory parameters for which the most patients had new or worsening findings were low neutrophils, low lymphocytes, low platelets, low leukocytes and elevated glucose [Younes 2012].

Most patients in the two phase 2 studies were between the ages of 18 and 65 years; as a result, there are limited data available regarding the use of brentuximab vedotin in elderly patients. In addition, the maximum number of cycles administered in the pivotal phase 2 studies was 16 and it is unknown whether there is any change in the safety profile of brentuximab vedotin

Confidential. Page 14 of 44

with longer term use or with the implementation of the recommended dose reductions in the presence of specific toxicities.

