4.2.1 Inclusion Criteria

To be eligible for enrolment, patients must meet all of the following criteria:

- Age at enrolment ≥ 18 years
- Clinical diagnosis (with histologic confirmation) of relapsed or refractory CD30+ HL or relapsed or refractory sALCL
- Patient is planned to start or is already receiving single agent therapy with brentuximab vedotin as part of routine clinical care

Confidential. Page 16 of 44

• Willing and able to provide informed consent

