4.3 Exposure Definition and Measures

This is an observational study of real-world treatment practices in this patient population. This protocol does not recommend the use of any specific treatments. No study medication is provided as part of participation.

Patients will be enrolled after the patient agrees to participate and signs the informed consent form. All exposure to brentuximab vedotin (including any exposure prior to enrolment) will be collected.

As an observational study to understand safety in patients treated in the post-marketing setting, no restrictions on concomitant treatments are associated with the study. All concomitant treatments (and subsequent treatments for lymphoma during follow-up) will be carefully recorded in order to evaluate their potential influence on the outcomes of interest.

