4.5 Data Collection

4.5.1 Schedule of Recommended Recording of Essential Data

Essential data for the study are presented in the Schedule of Recommended Recording Essential Data provided in Table 1. For eligible patients who provide informed consent, data elements will be abstracted from information routinely recorded in the medical record. Follow-up data will be collected in conjunction with all routine care visits, typically occurring at approximately every three months. No study visits or examinations, laboratory tests or procedures are mandated as part of this study.

Confidential. Page 19 of 44

Table 1 Schedule of Recommended Recording of Essential Data

	Enrolmenta	On-Treatment Follow- up ^b	Post-Treatment Follow-up ^c (or study discontinuation)
Informed consent	X		
Demography	X		
Patient height & weight	X	X (weight only)	
ECOG Performance Status	X	X	
Relevant medical history & co-morbidities	X	X	
Laboratory test results (if performed as part of routine care)	X	X	
Relapsed or refractory CD30+ HL or sALCL disease and treatment history	X	X	
Brentuximab vedotin treatment details	X	X	
Concomitant medications	X	X	
Changes in treatment, including dose modifications		X	
Survival status			X
SAE and AESI recording in eCRF (Refer to section 7.2) ^d	X	X	
Both SAEs and AESI considered related to brentuximab vedotin - recording in eCRF (Refer to Section 7.2) ^d			X
Date and reason for discontinuation (if applicable)		X ^e	X ^e

^a Exposure to brentuximab vedotin may have started prior to enrolment. All brentuximab vedotin treatment and concomitant medication exposures, SAEs/AESI and relevant medical history since starting the current brentuximab vedotin regimen should be recorded at the time of enrolment.

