4.5.2 Baseline/Enrolment

The following data will be recorded, where available, at baseline for all enrolled patients:

- Demographics [date of birth, sex, race/ethnicity (where allowed by local regulations)]
- Weight, height (calculated BMI)
- ECOG performance status
- Relevant medical history, including cardiovascular (e.g., congestive heart failure, rhythm abnormalities), diabetes, pulmonary (e.g., chronic obstructive pulmonary

Confidential. Page 20 of 44

^b The On-Treatment period is defined as beginning at the time of enrolment and continuing through 30 days after the last dose of brentuximab vedotin.

^c The Post-Treatment Follow-up period is defined as beginning 31 days after the last dose of brentuximab vedotin and continuing until study discontinuation.

^d Refer to Section 7.2 for the procedures for recording and reporting SAEs and both serious and non-serious, AFSIs

^e Refer to section 4.5.4 for a listing of data to be recorded at the time of study discontinuation.

disease), hepatic, renal, other malignancies, neurologic (e.g., neuropathies), autoimmune disease, infectious disease (e.g., HIV, Epstein Barr virus), abnormal blood counts (cytopenias and growth factor exposure), thyroid dysfunction

- Relevant laboratory testing [e.g., haematology, lactate dehydrogenase (LDH), CD30 expression %], if performed as part of routine care
- CD30+ HL or sALCL disease and treatment history
 - o Disease type (CD30+ HL or sALCL)
 - o Date of initial diagnosis
 - Diagnostic testing performed
 - o Disease stage
 - Presence of lymphoma-related symptoms (B symptoms)
 - o Extent of disease determined by both physical examination and imaging
 - o ALK status (positive, negative, unknown) (sALCL patients only)
 - o ALCL variant: common, small cell, lymphohistiocytic, sarcomatoid, other, unknown (sALCL patients only)
 - o HL subtype: nodular sclerosing, mixed cellularity, lymphocyte-rich, lymphocyte depleted, unspecified/unknown
 - o Previous treatment
 - Previous lines of therapy, with number of cycles
 - Autologous stem cell transplant or allogeneic stem cell transplant
 - Radiation therapy
- Brentuximab vedotin treatment, including dose and treatment date for current regimen and any changes in treatment dose prior to enrolment
- Occurrence of SAEs and both serious and non-serious AESI (per Section 7.2 Procedures for Recording and Reporting SAEs and AESI) since start of current treatment regimen of brentuximab vedotin
- Concomitant medications

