7.2.1 Events to be recorded in the eCRF

All SAEs and both serious and non-serious AESI will be recorded in the eCRF, from the patient's first dose of brentuximab vedotin through 30 days after the patient's last dose of brentuximab vedotin. For retrospectively enrolled patients, this includes any SAEs or both serious and non-serious AESI identified in the medical record which occurred prior to study enrolment but after initiating the current regimen of brentuximab vedotin. From 31 days after the patient's last dose of brentuximab vedotin, only SAEs and both serious and non-serious AESI considered related to brentuximab vedotin will be recorded in the eCRF (see Table 3).

Documentation regarding an SAE or both serious and non-serious AESI, observed by the investigator or reported by the patient upon indirect questioning, should be made as to the

Confidential. Page 31 of 44

nature, date of onset, end date, severity, relationship to brentuximab vedotin, action(s) taken, and outcome.

If any of the same SAE or both serious and non-serious AESI, occur on several occasions in the same patient, then the event in question must be documented and assessed each time.

7.2.2 Events to be reported to Millennium Pharmacovigilance & Risk Management (PV&RM) or designee (in addition to being recorded in the eCRF)

All SAEs (regardless of relationship to brentuximab vedotin) and both serious and non-serious AESI considered related to brentuximab vedotin, occurring from the patient's first dose of brentuximab vedotin in the current regimen through 30 days after the patient's last dose of brentuximab vedotin, must also be reported to Millennium PV&RM or designee by faxing a completed SAE Form within one business day after becoming aware of the event (see Table 3). For retrospectively enrolled patients, this includes any SAEs (regardless of relationship to brentuximab vedotin) or AESI, both serious and non-serious, considered related to brentuximab vedotin identified in the medical record which occurred prior to study enrolment but after initiating the current regimen of brentuximab vedotin.

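### Section 4.3 promises all brentuximab vedotin exposure, but the baseline items request dose and dates only from the start of the current regimen, so cumulative dose cannot be derived for re-treated patients

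*Protocol*

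**What the plan says.** Section 4.3 is unqualified: "All exposure to brentuximab vedotin (including any exposure prior to enrolment) will be collected".

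The operational text is narrower. Section 4.5.2 lists "Brentuximab vedotin treatment, including dose and treatment date for current regimen and any changes in treatment dose prior to enrolment". Table 1 footnote a says that treatment, concomitant medication, events and relevant history "since starting the current brentuximab vedotin regimen should be recorded at the time of enrolment". For retrospectively enrolled patients, Section 7.2.1 takes in pre-enrolment events that "occurred prior to study enrolment but after initiating the current regimen of brentuximab vedotin".

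The drug-related entry criterion in Section 4.2.1 is "Patient is planned to start or is already receiving single agent therapy with brentuximab vedotin as part of routine clinical care". Neither it nor the exclusions in Section 4.2.2 require that a patient has never had the drug.

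Two other items in Section 4.5.2 could pick up traces of an earlier course: "Previous lines of therapy, with number of cycles", and a neurologic history item, "neurologic (e.g., neuropathies), autoimmune disease, infectious disease". The whole list applies only where the data are available.

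On the phase 2 studies, the Background describes neuropathy "with an onset and severity pattern consistent with a cumulative effect of exposure".

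**The concern.** Section 4.3 and the data list give different answers to what a site should record for a patient who had an earlier course. Sites abstract from the list and the schedule, so the narrower request is likely to prevail. The repeated reference to a current regimen at least allows for an earlier one.

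The second objective is to identify and describe risk factors for neuropathy, and longer-term exposure is a named question in Section 2, Section 4.4.1 and Section 5.2.1. Both concern the amount of drug a patient has received. Section 5.2.4 itself concedes that earlier regimens may substantially affect neuropathy risk. An earlier course of the same drug is the most direct case, yet its dose and dates are not requested.

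This belongs in the protocol because a later analysis plan can define variables but cannot recover dose and dates that were never collected.

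**Working it through.** The plan has no figure that this point would change. Table 2 (precision at 500 patients) is unaffected. The check is a comparison of the texts, followed by arithmetic that is illustrative only.

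**1. What can be derived for an earlier course from the listed items**

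| Quantity | Item that could supply it | Derivable? |
|---|---|---|
| That an earlier course took place | Previous lines of therapy | Yes, where available; the drug is not named in the item |
| Number of earlier cycles | Same item | Yes, where available |
| Dose received | None | No |
| Start and stop dates | None | No |
| Cumulative dose over all courses | Needs dose | No |
| Interval from earlier to current course | Needs stop date | No |
| Neuropathy at first dose of the current regimen | Neurologic history | Partly; status at that date is not specified |

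**2. Terms left open**

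- Section 5.2.2.1 runs time at risk from first to last dose plus 30 days, without saying whether the first dose is the first ever or the first of the current regimen.
- Section 7.2.2 ties reporting to the first dose in the current regimen. Section 4.5.2 asks for events since that regimen began.
- Sections 4.4.1 and 5.2.1 define the long-exposure group as more than 16 cycles, without saying whether over one course or all. The by-cycle display in Section 5.2.2.1 is equally open.

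**3. Why the cycle definition matters (illustration)**

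Inputs: phase 2 median exposure of 9 cycles in HL and 6 in sALCL (Background). Assumption: one earlier course of that length. The first cycle above 16 is the 17th.

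- HL: 17 − 9 = 8. Counted over all courses, the patient enters the long-exposure group at current cycle 8.
- sALCL: 17 − 6 = 11. The patient enters at current cycle 11.

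Counted over the current regimen alone, the same patients are outside the group at those points.

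**4. Why the first-dose definition matters (illustration)**

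Assumption: two courses, each of the HL median of 27 weeks (27 × 7 = 189 days), with a gap of G days.

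- From the first dose of the current regimen: 189 + 30 = 219 days at risk.
- From the first dose ever: 189 + G + 189 + 30 = 408 + G days at risk.

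Even at G = 0 the ratio is 408 / 219 = 1.86, while the events requested still come from the current regimen only. Under the first-ever reading, such a patient's denominator would grow without matching events.

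**5. How many patients**

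The protocol gives no share. For assumed shares of 1%, 2%, 5% and 10%: 500 × 0.01 = 5, 500 × 0.02 = 10, 500 × 0.05 = 25 and 500 × 0.10 = 50.

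**The case against.** The strongest reply is that there is no real contradiction. Section 4.5.2 introduces the current regimen with the word including, which does not shut out other courses. Footnote a attaches the same window to relevant medical history, yet Section 4.5.2 plainly collects older history, so the footnote may be a minimum look-back for patients enrolled after starting treatment. The promise in Section 4.3 may likewise mean only doses of the current course given before consent. This has force, and it makes the conflict a matter of wording. It does not close the gap: on every reading, no item asks for the dose or dates of an earlier course.

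A reader might infer more: that re-treated patients are analysed as if in their first cycle, that early-cycle neuropathy is therefore inflated, that patients passing 16 cycles over two courses are misclassified, and that prior neuropathy becomes a false risk factor. The protocol does not support these inferences:

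- No section restarts the cycle count, and the previous-lines item can supply earlier cycles where available.
- Whether two separated courses make up long-term treatment is a matter of definition. Not adding them is not in itself an error.
- Under Section 7.1, a prior condition that is unchanged or improved is not an adverse event, and the Cox outcome is new or worsened neuropathy. Residual neuropathy counts only if it worsens.
- Section 5.2.2.1 leaves the specific risk factors to the analysis plan. Prior neuropathy is a legitimate descriptive factor whatever caused it.

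**Conclusion.** The point holds as a gap in data capture with undefined terms attached, and it merits correction at modest priority. Section 4.3 and the baseline items need reconciling. As listed, the items do not allow cumulative dose or the interval since an earlier course to be derived for re-treated patients, who are eligible, for an outcome that the protocol itself describes as cumulative.

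The size is unknown. It depends on the re-treated share, which the protocol does not give; the 5 to 50 patients above rest on assumed shares. The cycle and person-time examples show what the open definitions could do to one patient, not a bias in any planned result. The point assumes that sites record what the list asks for and little beyond it. The choice of Cox covariates may properly wait for the analysis plan.

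**What to change.** 1. In Section 4.5.2 and Table 1 footnote a, add for any earlier brentuximab vedotin course: start and stop dates, number of cycles, dose received, and whether neuropathy was present at the first dose of the current regimen. This brings both into line with Section 4.3.
2. In Section 5.2.2.1, state that the first dose for time at risk is the first dose of the current regimen, matching the event window in Section 7.2.
3. State whether cycle number and the more-than-16-cycles group are counted over the current regimen or over all courses.
4. Show neuropathy results for patients without an earlier course, with re-treated patients presented separately.

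The cost is a few eCRF fields from records already being abstracted, two definitions and one extra display. Since enrolment began in June 2013 and this amendment is dated March 2014, the fields would also have to be completed for patients already enrolled. Some earlier-course data may be unavailable and should be reported as missing. Nothing in the change affects treatment.

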4.5.3 On-Treatment Follow-up

The following data will be recorded, where available, for all enrolled patients at each follow-up time point through 30 days after the last dose of brentuximab vedotin.:

- Visit date
- Current weight (kg)
- ECOG (if recorded)/Survival status
 - o Date and cause of death, if applicable
- New onset co-morbidities and updated medical history, including development of secondary malignancies, risk factors for neuropathy and status of neuropathy if ongoing at end of treatment with brentuximab vedotin
- Updated treatment status
 - o Brentuximab vedotin cycles
 - dose changes/discontinuations, change type, date (or duration) of change and reason for change
 - o Any newly initiated lines of therapy
 - o Radiation therapy

Confidential. Page 21 of 44

- Stem cell transplant (enrolling sites will be expected to continue to provide follow-up data in the event the patient temporarily transfers to another healthcare provider for the purpose of autologous or allogeneic SCT)
- Concomitant medications
- Relevant laboratory testing
- Occurrence of SAEs and both serious and non-serious AESI(per Section 7.2 Procedures for Recording and Reporting SAEs and AESI), since last follow-up

4.5.4 Post-Treatment Follow-up

The following data will be recorded, where available, in the post-treatment follow-up period:

- SAEs considered related to brentuximab vedotin
- AESI, both serious and non-serious, considered related to brentuximab vedotin

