Study design: This is a multi-centre prospective, observational cohort study of the safety of brentuximab vedotin treatment in patients who have been diagnosed with relapsed or refractory CD30+ HL or relapsed or refractory sALCL. The study will target the enrolment of approximately 500 patients (at least 50 of whom have a diagnosis of sALCL), who are treated with brentuximab vedotin at approximately 75-100 sites in Europe and potentially other countries outside of Europe. Patients will be enrolled over an approximate 3-year enrolment period and the total study duration will be five years from the date of first patient enrolled. Patients already being treated with brentuximab vedotin at the time of enrolment will be considered to be retrospectively enrolled for purposes of analysis and inclusion in the PASS.

Study population:

Inclusion criteria

- Age at enrolment \geq 18 years
- Clinical diagnosis (with histologic confirmation) of relapsed or refractory CD 30+ HL or relapsed or refractory sALCL
- Patient is planned to start or is already receiving single agent therapy with brentuximab vedotin as part of routine clinical care
- Willing and able to provide informed consent

Exclusion criteria

- Concurrent participation in an interventional clinical study
- Patients with primary cutaneous ALCL, unless the disease has transformed to systemic ALCL

Data collection: Data elements will be collected from information routinely recorded in the medical record. No study visits or examinations, laboratory tests or procedures are mandated by the study. Baseline patient and disease characteristics, relevant medical history and all initial and subsequent treatment for relapsed or refractory CD30+ HL or relapsed or refractory sALCL will be recorded. Follow-up will include changes in patient status and disease management, treatment with brentuximab and any other medications, SAEs and both serious and non-serious AESI [i.e., peripheral neuropathy, neutropenia (including febrile neutropenia), infections (including opportunistic infections), hyperglycaemia and hypersensitivity reactions (including infusion-related reactions or allergic reactions)], as assessed by the treating physician. Patients will remain under follow-up until death, withdrawal of consent, loss of follow-up or study closure, whichever comes first. Follow-up data will be collected in conjunction with all routine care visits, typically every three months.

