5.2.2 Planned analyses

5.2.2.1 Primary analyses

Serious Adverse Events (SAEs) and Adverse Events of Special Interest (AESI)

SAEs and AESI (including both serious and non-serious AESI) will be summarized by MedDRA system organ class (SOC) and preferred term (PT). Frequency and incidence proportion for all SAEs and AESI (as defined in Section 4.4.1) will be reported for patients who received at least one dose of brentuximab vedotin while on study.

The incidence rate and the associated 95% CI will be reported for SAEs and AESI.

Time at risk of SAEs and AESI will correspond to current/recent treatment with brentuximab vedotin. Current/recent treatment will be defined as time between the dates of first and last dose plus 30 days. All other follow-up time accrued for the patient will be considered occurring during past treatment with brentuximab vedotin; events reported during the past treatment period will be presented separately.

In addition, select events will be displayed by timing in relation to treatment start (e.g., by number of completed cycles) or time-to-event analysis may be carried out using Kaplan-Meier plots for the occurrence of the first reported occurrence of the adverse event, as appropriate for the event.

Identification and Description of Risk Factors for Peripheral Neuropathy

In addition, multivariable adjusted analysis will be performed to identify and describe risk factors for peripheral neuropathy (e.g., BMI, previous history of neuropathy, known toxic exposures) in the cohort. Risk factors for the first occurrence of new onset or worsening of peripheral neuropathy will be explored using a multivariable adjusted Cox regression model. Model assumptions concerning proportionality will be evaluated graphically in the usual manner. The inclusion of specific risk factors will be described in the SAP. A preliminary univariate analysis of the association of variables of interest with the outcome measure will be

Confidential. Page 24 of 44

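### Section 4.3 promises to record later lymphoma treatment during follow-up, but the collection schedule specifies it only to 30 days after the last dose, so late related events cannot be systematically related to the next therapy

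*Protocol*

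**What the plan says.** **The undertaking.** Protocol Section 4.3 states: "All concomitant treatments (and subsequent treatments for lymphoma during follow-up) will be carefully recorded in order to evaluate their potential influence", the influence meant being that on the outcomes of interest. The synopsis (Data collection) has a related sentence: "all initial and subsequent treatment for relapsed or refractory CD30+ HL or relapsed or refractory sALCL will be recorded". It adds that follow-up covers changes in disease management and other medications, and that patients stay under follow-up until death, withdrawal of consent, loss or study closure.

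**The schedule.** Section 4.5.3 lists new lines of therapy, radiation, stem cell transplant and concomitant medications. Its scope is "at each follow-up time point through 30 days after the last dose of brentuximab vedotin". For the time after that, Section 4.5.4 begins "The following data will be recorded, where available, in the post-treatment follow-up period" and lists two items: related SAEs and related AESI. In Table 1 the row "Relapsed or refractory CD30+ HL or sALCL disease and treatment history" is marked at enrolment and on treatment but not after treatment. The same holds for concomitant medications, and changes in treatment are marked on treatment only.

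**The analysis.** Section 5.2.2.1 defines time at risk as first to last dose plus 30 days and treats all later follow-up as past treatment, where "events reported during the past treatment period will be presented separately".

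**The concern.** The protocol gives a reason for collecting later lymphoma therapy, then specifies a schedule that stops collecting it 30 days after the last dose. Patients are enrolled on single-agent brentuximab vedotin, so a next systemic line or a transplant can be expected to come after it ends. Infection, neutropenia and neuropathy may plausibly also follow chemotherapy or transplant.

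After day 30 an event enters the database only if the investigator answers yes to the relatedness question in Section 7.1. Without the type and start date of the next therapy in the dataset, the past-treatment table cannot be divided into events before and after that therapy, and the relatedness judgements cannot be examined against it in a uniform way. This is not a detail that the SAP can settle, because an SAP cannot analyse data that the schedule does not ask for.

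**Working it through.** No stated figure is in dispute. The check is a comparison of the sections, followed by arithmetic on how much follow-up time is concerned.

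**Step 1: what is specified, by period.**

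| Item | On treatment (to last dose + 30 days) | Post-treatment (from day 31) |
|---|---|---|
| New lines of therapy, radiation, transplant | Section 4.5.3 | not listed |
| Disease and treatment history | Table 1 | no mark |
| Concomitant medications | Section 4.5.3, Table 1 | no mark |
| Changes in treatment | Section 4.5.3, Table 1 | no mark |
| SAEs and AESI | all | related only |
| Survival status | Section 4.5.3 | Table 1 |
| Date and reason for discontinuation | Table 1 | Table 1 |

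**Step 2: does another section close the gap?**

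- Section 4.2.4 says patients who stop brentuximab vedotin are followed according to this same schedule. It also asks, if possible, for a final check of treatment status when a patient withdraws and the last assessment is more than three months old. That is one conditional contact for withdrawing patients, and no therapy type or start date is specified.
- Section 4.5.5 refers back to Table 1 according to period, so it adds no therapy item for a post-treatment patient.
- Section 7.2.1 lists what is documented for each event. Other lymphoma therapy is not in that list.
- The sentence in Section 4.5.3 on continued data when a patient transfers for transplant sits in the on-treatment list and does not lengthen the window.

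None of these restores what Section 4.3 promises.

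**Step 3: how much follow-up time lies outside the window.** Inputs from the protocol:

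- enrolment of about 3 years and total duration of 5 years (synopsis, Study design);
- median phase 2 exposure of 27 weeks in HL and 20 weeks in sALCL (Section 1);
- a window that closes 30 days after the last dose, that is 30/7 = 4.3 weeks.

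Assumptions: uniform enrolment, phase 2 medians standing for on-treatment time, no death or loss.

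- Mean potential follow-up: 60 − 36/2 = 42 months = 182.6 weeks. Last patient enrolled: 60 − 36 = 24 months = 104.4 weeks.
- Window with therapy collection: 27 + 4.3 = 31.3 weeks (HL); 20 + 4.3 = 24.3 weeks (sALCL).
- Share outside the window = 1 − window / potential follow-up.

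| Potential follow-up | HL | sALCL |
|---|---|---|
| 42 months | 1 − 31.3/182.6 = 82.9% | 1 − 24.3/182.6 = 86.7% |
| 24 months | 1 − 31.3/104.4 = 70.0% | 1 − 24.3/104.4 = 76.7% |

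The milestones (June 2013 to March 2018) give 57 months rather than 60. Mean potential follow-up is then 57 − 18 = 39 months = 169.6 weeks, and the shares are 1 − 31.3/169.6 = 81.5% (HL) and 1 − 24.3/169.6 = 85.7% (sALCL). The picture does not change.

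**The case against.** Several points on the other side stand and limit the finding.

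- **The main analysis is untouched.** The first objective concerns actively treated patients, and time at risk ends 30 days after the last dose. A reader might infer that the study's incidence proportions and rates are compromised. They are not: past-treatment events are kept apart, and only those judged related are recorded.
- **There is a case-level route.** After day 30, Table 3 has the same events recorded and reported. Each goes on an SAE Form, Section 7.2.2 allows the sponsor to request follow-up information, and under Section 6.4 monitors may check original records. It would be too strong to say that late events can never be read against the next therapy. What is missing is a specified, structured item for every patient, including those with no event.
- **The percentages measure time.** A reader might take 70-87% as the share of next therapies or events missed. The protocol gives no interval from last dose to next therapy, therapy begun within 30 days is captured by Section 4.5.3, and death or loss would shorten the later period.
- **The synopsis sentence is weaker support than it looks.** It opens with baseline characteristics and can be read as prior treatment history. The promise rests mainly on Section 4.3.
- **Section 4.5.4 may simply be incomplete.** It omits survival status, which Table 1 marks after treatment, and Table 1 is a schedule of recommended, essential data. The eCRF is not shown and may hold more. That may explain the contradiction but does not remove it, since sites work from the schedule as written.

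**Conclusion.** The contradiction holds. Section 4.3 says later lymphoma treatment is recorded during follow-up in order to evaluate its influence. Table 1 and Sections 4.5.3 and 4.5.4 specify it only to 30 days after the last dose, and Sections 4.2.4 and 4.5.5 do not repair this.

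The consequence is confined to the past-treatment related SAEs and AESI. As specified, they cannot be systematically related to the next therapy, so the evaluation promised in Section 4.3 has no specified data for that period. The on-treatment estimates stand.

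The period concerned is about 70-87% of potential follow-up time for 24 to 42 months of potential follow-up, under the assumptions stated above. The number of therapies or events affected cannot be derived from the protocol. The point merits a correction but does not threaten the study's main result.

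**What to change.** Reconcile Section 4.3 and the synopsis with Table 1 and Sections 4.5.3 and 4.5.4:

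- Add to Section 4.5.4, and to the post-treatment column of Table 1, the type and start date of each new lymphoma therapy: systemic line, radiation, autologous or allogeneic transplant.
- Extend the sentence on data from patients who transfer for transplant so that it also covers the post-treatment period.

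Past-treatment events can then be shown before and after the first new therapy; how to tabulate them can be left to the SAP. Narrowing Section 4.3 to the on-treatment period would also end the contradiction, but it would give up the stated evaluation.

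The cost is a protocol amendment and a few eCRF fields, completed from the medical record at routine contacts that already take place about every three months. No visit or test is added. Enrolment began in June 2013, so patients already off treatment would need limited back-collection.
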